#### **4.9 Study drug administration/compliance rate**

Drug administration/compliance rate (%) = Number of days of study drug use (administration)/(Period of study drug use [administration] – Number of days of drug interruptions) × 100

However, if the compliance rate exceeds 100%, it should be 100%.

#### **4.10 Mean daily dose/mean weekly dose**

Mean daily dose of MT-6548 during each scheduled study visit period\* = Daily dose based on the physician's prescription × Period of administration (days)\*3 of the corresponding dose\*2 between the scheduled study visits\*/Period between the scheduled study visits (days)\*4

Mean weekly dose of darbepoetin alfa during each scheduled study visit period\* = Daily dose based on the physician's prescription  $\times$  Period of administration (days)\*5 of the corresponding dose\*2 between the scheduled study visits\*/Period between the scheduled study visits (days)\*4  $\times$  7

\*: For each period between the scheduled study visits, the actual study visit dates will not be considered, and this variable should be fixed as follows:

- ✓ The first day of the treatment period to Week 2 of the treatment period: The first day of the treatment period (Day 1) to Day 14
- ✓ Week 2 of the treatment period to Week 4 of the treatment period: Days 15 to 28
- ✓ The same shall apply thereafter, and the final period between the scheduled study visits should be Week 20 to Week 24 of the treatment period: Day 141 to a blood sampling day for hematology tests at Week 24 of the treatment period.

However, for subjects who discontinued their treatment, the final period between the scheduled study visits should be up to the day before discontinuation.

\*: If there are multiple applicable doses, the sum of the calculated values for each dose should be used.

\*: The number of days without drug administration other than drug interruption should not be excluded from the "period of administration (days)."

\*: 14 days up to Week 12 of the treatment period and 28 days after Week 12 of the treatment period. However, for subjects who discontinued their treatment, the final period between the scheduled study visits (days) should be the actual number of days until the day before discontinuation.

\*: "Period from the day of administration of darbepoetin alfa to the day of next administration of darbepoetin alfa." However, the first treatment period (days) during the scheduled study visit period should be "period from the start date during the scheduled study visit period to the day before the day of the first darbepoetin alfa administration date after the start date during the scheduled study visit period" and the last treatment period (days) should be "from the last day of darbepoetin alfa administration during the scheduled study visit period to the day before the day of the last treatment or the day before discontinuation during the scheduled study visit period."

The following formula should be used when no darbepoetin alfa is administered during the scheduled study visit period.

Mean weekly dose of darbepoetin alfa = Weekly dose of darbepoetin alfa immediately before the period between scheduled study visits

## 4.11 Cumulative dosage

The cumulative dosage of the study drug is defined by the following formula.

Confidential

Cumulative dosage of MT-6548 =  $150 \text{ mg} \times \text{Days of } 150 \text{ mg administration} + 300 \text{ mg} \times \text{Days of } 300 \text{ mg administration} + 450 \text{ mg} \times \text{Days of } 450 \text{ mg administration} + 600 \text{ mg} \times \text{Days of } 600 \text{ mg administration}$

Number of administration days of X mg\* = Day when dose was changed from X mg – First day of X mg administration (not excluding the number of days of no drug administration)

If there are multiple applicable periods, the sum of them should be used.

\*: X indicates each dose of MT-6548.

The cumulative dosage of darbepoetin alfa is the sum of individual doses of darbepoetin alfa  $\times$  the number of administrations of individual doses.

## 4.12 Adverse drug reactions

In the MT-6548 group, adverse events for which a causal relationship to MT-6548 tablets is evaluated as “reasonably possible” are defined as adverse drug reactions associated with MT-6548 tablets, and in the darbepoetin group, adverse events for which a causal relationship to darbepoetin alfa injection is evaluated as “reasonably possible” are defined as adverse drug reactions associated with darbepoetin alfa injection.

## 4.13 Iron supplement dosage

The dose of iron supplements is defined by the following formula. However, the dose of iron supplements will not be calculated if iron supplements are used as needed.

Mean monthly dose of iron supplements during the screening period\* and each scheduled study visit period\* (tabulation period of iron supplements) = (Daily dose based on the physician's prescription  $\times$  Period of administration (days) of the corresponding dose\* during the tabulation period of iron supplements)/Tabulation period of iron supplements (days)\*  $\times$  30.4375\*

\*: The number of days of the screening period is “First day of the treatment period – First day of the screening period.”

\*: For each period between the scheduled study visits, the actual study visit dates are not considered, and this tabulation is fixed as follows:

- ✓ The first day of the treatment period to Week 2 of the treatment period: The first day of the treatment period (Day 1) to Day 14
- ✓ Week 2 of the treatment period to Week 4 of the treatment period: Days 15 to 28
- ✓ The same shall apply thereafter, and the final period between the scheduled study visits should be Week 20 to Week 24 of the treatment period: Day 141 to a blood sampling day for hematology

tests at Week 24 of the treatment period. However, for subjects who discontinued their treatment, the final period between the scheduled study visits should be up to the day before discontinuation.

\*: If there are multiple applicable doses, the sum of the calculated values for each dose should be used.

\*: For subjects who discontinued their treatment, the final period between the scheduled study visits (days) should be the actual number of days until the day before discontinuation.

\*: In this tabulation, 1 month is counted as 30.4375 days (365.25/12 = 30.4375).

#### 4.14 Kt/V

Kt/V is defined by the following equation. It is calculated based on the first day of treatment period, Week 24, and the day of discontinuation. All items used for the calculation of Kt/V should be those measured on the same day.

$$Kt/V = -\ln(Ct/C0 - 0.008 \times t) + (4 - 3.5 \times Ct/C0) \times (BW0 - BWt)/(BWt)$$

t: Dialysis time, C0: BUN concentration before dialysis, Ct: BUN concentration after dialysis, BW0: Body weight before dialysis, BWt: Body weight after dialysis

#### 4.15 QOL (EQ-5D-5L) index value

Responses to 5 questions (mobility [Mo], self care [Sc], usual activities [Ua], pain/discomfort [Pd], anxiety/depression [Ad] in 5 levels (level 1 is healthy and the level goes up to 5, and the health status decreases with increases in level) are converted into index values. The index value is calculated using the Japanese EQ-5D-5L conversion table (Table 4.14.1).[1]

- (1) The responses to questions from Mo to Ad should be arranged side by side into five numbers (hereinafter, health state). The health state can exist from “11111” to “55555.”
- (2) If all five responses are 1, i.e. the health state is “11111”, the index value is 1. If the health state is other than “11111,” “Constant term: -0.060924” in Table 4.14.1 and the estimated value of the coefficient for each level of the response to each question should be used to obtain the index value using the following formula. The index value of the subject should be missing if one of the 5 questions has not been answered.

Index value = 1 + “Estimate of the constant term” + “Sum of ‘estimated coefficients corresponding to levels of responses other than 1’”

Table 4.14.1 Japanese EQ-5D-5L conversion table

Item	Level	Estimate	Standard error	p value
Constant term		-0.060924	0.013625	<0.0001
Mo	2	-0.063865	0.008996	<0.0001
	3	-0.112618	0.009287	<0.0001
	4	-0.179043	0.010231	<0.0001
	5	-0.242916	0.009425	<0.0001
Sc	2	-0.043632	0.008931	<0.0001
	3	-0.076660	0.009972	<0.0001
	4	-0.124265	0.010129	<0.0001
	5	-0.159659	0.008924	<0.0001
Ua	2	-0.050407	0.009205	<0.0001
	3	-0.091131	0.010005	<0.0001
	4	-0.147929	0.009744	<0.0001
	5	-0.174786	0.009115	<0.0001
Pd	2	-0.044545	0.008354	<0.0001
	3	-0.068178	0.010052	<0.0001
	4	-0.131436	0.008985	<0.0001
	5	-0.191203	0.009604	<0.0001
Ad	2	-0.071779	0.009701	<0.0001
	3	-0.110496	0.010863	<0.0001
	4	-0.168171	0.009850	<0.0001
	5	-0.195961	0.009164	<0.0001

Mo: mobility, Sc: self care, Ua: usual activities, Pd: pain/discomfort, Ad: anxiety/depression

## 4.16 QOL (KDQOL) scoring

Step 1 (See Table 4.15.1): The appropriate score is converted from the response choices for each item number in Table 4.15.1 for each subject.

Table 4.15.1 Step 1 in KDQOL scoring 

Item number	Response choices	Score
Question 4 A–D	1	0
Question 5 A–C, Question 21	2	100
Question 3 A–J	1	0
	2	50
	3	100
Question 19 A, B	1	0
	2	33.33

	3	66.66
	4	100
Question 10	1	0
Question 11 A, C	2	25
Question 12 A–D	3	50
	4	75
	5	100
Question 9 B, C, F, G, I	1	0
Question 18 B	2	20
	3	40
	4	60
	5	80
	6	100
Question 20	1	100
	2	0
Question 1, Question 2, Question 6, Question 8	1	100
Question 11 B, D, Question 14 A–M	2	75
Question 15 A–H, Question 16 A, B	3	50
Question 24 A, B	4	25
	5	0
Question 7	1	100
Question 9 A, D, E, H	2	80
Question 13 A–F	3	60
Question 18 A, C	4	40
	5	20
	6	0
Question 23	1	100
	2	83.33
	3	66.66
	4	50
	5	33.33
	6	16.66
	7	0

Step 2 (See Table 4.15.2): The mean of the scores calculated at Step 1 in the item numbers in the right column of Table 4.15.2 should be calculated for each subject by subscale. For questions 17 and 22, the scores obtained are multiplied by 10 to convert the values from 0 to 100. The mean value should be the score for each subject by subscale. If at least one question constituting the subscale is answered, the subscale should be tabulated without missing. If “No” is chosen in question 16, the question 16 should be treated as missing.

Table 4.15.2 Step 2 in KDQOL scoring

- Each item score should be averaged to calculate each subscale score

Subscale	Number of items	After scoring according to Table 4-1, the mean of the items included in each subscale should be calculated.
Kidney disease-specific scale		
Symptoms	12	Questions 14 A–K, L (M)*
Effects of kidney disease on daily life	8	Question 15 A–H

Burden due to kidney disease	4	Question 12 A–D
Working status	2	Question 20, Question 21
Cognitive function	3	Question 13 B, D, F
Relationship with people	3	Question 13 A, C, E
Sexual function	2	Question 16 A, B
Sleep	4	Question 17, Question 18 A–C
Social support	2	Question 19 A, B
Encouragement from dialysis staff	2	Question 24 A, B
Patient satisfaction with dialysis care	1	Question 23
Comprehensive scale (SF-36)		
Physical functioning	10	Question 3 A–J
Daily role functioning (physical)	4	Question 4 A–D
Bodily pain	2	Question 7, Question 8
General health	5	Question 1, Question 11 A–D
Vitality	4	Question 9 A, E, G, I
Social functioning	2	Question 6, Question 10
Daily role functioning (emotional)	3	Question 5 A–C
Mental health	5	Question 9 B, C, D, F, H

## 5. Analysis Sets

Efficacy analysis will be performed in the full analysis set (hereinafter, FAS). Primary endpoint analysis will also be performed with the set of subjects conforming to the study protocol, or the per-protocol set (hereinafter, PPS). Safety analysis will be performed in the safety analysis set. Pharmacokinetic analysis will be performed in the pharmacokinetics analysis set.

The analysis sets are defined below. Details of treatment of subjects regarding treatment period phase 1 fixed data and final fixed data will be determined by the sponsor by the time the data are fixed.

### 5.1 Efficacy analysis set

#### (1) FAS

The FAS consists of all randomly allocated subjects excluding the following subjects:

- ✓ Subjects who did not have anemia associated with HD-CKD
- ✓ Subjects who have never received a dose of the study drug
- ✓ Subjects with no post-randomization efficacy data

#### (2) PPS

PPS is defined as the analysis set consisting of subjects from the FAS excluding the following subjects:

- ✓ Subjects who deviated from inclusion criteria
- ✓ Subjects who met any of the exclusion criteria

- ✓ Subjects who violated rules concerning prohibited concomitant drugs or therapies
- ✓ Subjects with a <80% compliance rate for either MT-6548 150 mg tablets or darbepoetin alfa injection

## 5.2 Safety analysis set

Safety analysis set consists of all randomly allocated subjects excluding the following subjects:

- ✓ Subjects who have never received a dose of the study drug
- ✓ Subjects with no post-randomization safety data

## 5.3 Pharmacokinetics analysis set

Pharmacokinetics analysis set consists of all randomly allocated subjects excluding the following subjects:

- ✓ Subjects who have never received a dose of MT-6548 150 mg tablets
- ✓ Subjects with no post-randomization plasma drug concentration data

## 6. Patient Cohort

The patient cohort is defined as follows:

Conversion cohort: A group of patients who have received ESA formulations from 8 weeks prior to the first day of the screening period.

## 7. Data Handling

The fixed data of the treatment period phase 1 should be handled as follows: The handling of data other than the following (excluding handling of data related to pharmacokinetic assessment) should be decided in the case review meeting and specified in the statistical analysis plan that will be fixed finally by the data fixation.

### 7.1 Handling of missing data

If test measurements are missing or if problems with samples etc. result in invalid measurements or reference values, these should be handled as missing values. Derived variables should also be treated as missing if even a single test value or other data required for derivation is missing or not adopted.

### 7.2 Handling of data for tabulation at each evaluation time point

Data that meet the permitted range specified in the “Table 9.1-1 Permitted ranges for study visits” section of the study protocol should be used for the tabulation at each evaluation time point and should not be imputed with those outside the permitted range.

If there are multiple data within the permitted range, then the one closer to the reference date should be adopted. If the deviations from the reference date are the same, data for the efficacy and safety evaluations should be adopted before and after the reference date, respectively.

### **7.3 Handling of efficacy endpoints if rescue therapy is performed**

If rescue therapy is performed, data from the day after rescue therapy should not be used to assess efficacy.

### **7.4 Imputation of missing values**

The mixed model repeated measures (hereinafter, MMRM) used to analyze the primary efficacy endpoint should not use data imputing missing data. If there are missing values at the first day of the treatment period, data from the day closest to the first day of the treatment period should be used as data for the first day of the treatment period.

Mean Hb values at Weeks 20 and 24 of the treatment period should be derived as data for analysis of covariance (hereinafter, ANCOVA), which is performed as a sensitivity analysis for the primary efficacy endpoint. Missing data are imputed with data from the evaluation time point immediately before the missing evaluation time point (excluding the first day of the treatment period) (hereinafter, LOCF method). When any one evaluation time points has missing values, the data at the evaluation time point closest to the missing evaluation time point is adopted, and when two evaluation time points have missing values, the data in the two different evaluation time points closest to and before the missing evaluation time points should be adopted to calculate the mean Hb value. However, Hb values at the same evaluation time point should not be used.

In addition, values imputed by the LOCF method at Week 24 of the treatment period should also be derived for clinical laboratory value, vital sign, QOL indices among the efficacy endpoints. Data obtained by imputing missing values at Week 24 of the treatment period should be used as data at the end of the treatment period phase 1.

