5.2 Study design

This is a multicenter, randomized, double-blind, active-controlled, double-dummy, parallel group comparative study.

(1) Screening period

The screening period begins on the first day of the screening period, and ends upon completion of tests required on the first day of the treatment period. Maximum screening period time is 6 weeks. Two visits will be made during the screening period; the first (SV1) is the first day of the screening period. The second screening period visit (SV2) occurs after results from laboratory tests performed on the first day of the screening period have been obtained. Testing may be repeated as necessary.

(2) Treatment period

The treatment period will last from completion of scheduled tests on the first day of the treatment period to completion of blood sampling for haematology tests on the final day of the treatment period (Week 52 of the treatment period or discontinuation of treatment).

The treatment period consists of phase 1 and phase 2, as defined below.

- ✓ Treatment period Phase 1: From completion of scheduled tests for the first day of the treatment period to completion of scheduled tests for Week 24 of the treatment period. Treatment period Phase 1 will be double-blind.
- ✓ Treatment period Phase 2: From the completion of the tests specified for Week 24 of the treatment period to the completion of tests specified for Week 52 of the treatment period. Even after all subjects complete the treatment period Phase I and the key

code is opened, the subjects, study institution staff members, and monitoring personnel will remain blinded to treatment. Details of the procedure of maintaining the blindness will be separately defined before opening of the key code.

During the treatment period, subjects are to visit the study site on the day of dialysis after a 2-day interdialytic interval; however, if this is difficult, subjects are to visit the study site on the day of dialysis after a 1-day interdialytic interval. After the first day of the treatment period, subjects are to visit the study site every 2 weeks until Week 12 and every 4 weeks after Week 12 to undergo the scheduled test. However, subjects are to visit the study site at shorter intervals as necessary, if excessive increases or decreases in Hb are of concern based on the time course of Hb levels, the dose interval of darbepoetin alfa injection is shorter than the scheduled visit interval, or for hemodialysis.

(3) Follow-up observation period

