9.2.3 Efficacy endpoints

Blood sampling will be performed at each study center for measurement by the contract laboratory testing facility. Study centers will store test reports issued by the contract testing laboratory. EPO measurements will be disclosed to the sponsor after key code opening, but will not be disclosed to subjects, study center staff, or monitoring staff until completion of the final data lock at the end of the study.

During the screening period, blood will be collected before dialysis whenever the subject makes a study visit on the same day they are scheduled for dialysis. During the treatment period, blood will be collected before dialysis on days the subject is scheduled for dialysis.

(1) Hb value

Blood sampling and Hb measurement will be performed in the supine position on the first day of the screening period, screening period Visit 2, the first day of the treatment period, Weeks 2, 4, 6, 8, 10, 12, 16, 20, 24, 28, 32, 36, 40, 44, 48, and 52 of the treatment period, and the day of discontinuation of treatment.

(2) Ratio of subjects who received ESA rescue therapy

If ESA rescue therapy is performed, type of ESA formulation used, administration route, dose interval, and dosage will be recorded in the CRF.

(3) Ratio of subjects who received red blood cell (RBC) transfusion rescue therapy.

If RBC transfusion rescue therapy is performed, type of RBC formulation used and dosage will be recorded in the CRF.

(4) Study drug dosage

Study drug dosage will be recorded in CRFs.

(5) Total number of dosage adjustments

Yes/no for MT-6548 dosage adjustments and post-adjustment dosage will be recorded in the CRF.

(6) Quantity of iron administered

Iron dosage will be recorded in CRFs.

(7) Iron-related measures (serum iron, TIBC, TSAT, and serum ferritin)

Blood sampling and measurement will be performed for serum iron, TIBC, TSAT, and serum ferritin on the first day of the screening period, the first day of the treatment period, Weeks 2, 4, 6, 8, 10, 12, 16, 20, 24, 28, 32, 36, 40, 44, 48, and 52 of the treatment period, and the day of discontinuation of treatment.

(8) Hepcidin

Blood sampling and measurement of hepcidin will be performed on the first day of the treatment period, treatment period Weeks 2, 4, 6, 12, 24, 36, and 52, and the day of discontinuation of treatment.

(9) Haematocrit, RBC count

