Blood sampling and measurement will be performed for haematocrit and RBC count on the first day of the screening period, the first day of the treatment period, Weeks 2, 4, 6, 8, 10, 12, 16, 20, 24, 28, 32, 36, 40, 44, 48, and 52 of the treatment period, and the day of discontinuation of treatment.

(10) Reticulocytes (counts and fractions)

Blood sampling and measurement will be performed for reticulocytes (counts and fractions) on the first day of the screening period, the first day of the treatment period, Weeks 2, 4, 6, 8, 10, 12, 16, 20, 24, 28, 32, 36, 40, 44, 48, and 52 of the treatment period, and the day of discontinuation of treatment.

(11) EPO

Blood sampling and measurement of EPO will be performed on the first day of the treatment period, treatment period Weeks 2, 4, 6, 12, 24, 36, and 52, and the day of discontinuation of treatment. Blood sampling time will be recorded in CRFs.

EPO measurements will be disclosed to the sponsor after key code opening, but will not be disclosed to subjects, study center staff, or monitoring staff until completion of the final data

lock at the end of the study. Study centers are prohibited from measuring EPO during the treatment period in order to maintain blinding.

(12) QOL measures (EQ-5D-5L, KDQOL)

Subjects will fill out EQ-5D-5L and KDQOL questionnaires (Appendices 4 and 5) on the first day of the treatment period, treatment period Weeks 12, 24, and 52, and the day of discontinuation of treatment, and results recorded in CRFs.

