- [q] MT-6548 tablets should be prescribed to subjects depending on the number of their unused tablets. Subjects should be instructed to use up one bottle before opening the next.

- [r] In principle, dosage adjustments should be performed at scheduled study visits or on the day of darbepoetin alfa injection; however, an additional visit may be provided for dosage adjustment, if considered necessary, in cases where excessive increases or decreases in Hb values are of concern based on the Hb time course.
- [s] The first dose should be administered after completion of the scheduled tests on the first day of the treatment period.
- [t] The first dose should be administered after completion of the scheduled tests on the first day of the treatment period. However, the tests scheduled after dialysis should be performed before the first dose whenever possible.

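### Section 7.4 of both SAPs lets an on-treatment value stand in for a missing baseline, distorting change from baseline for the subjects concerned

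*SAP*

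**What the plan says.** Both SAPs carry the same rule in section 7.4: for a missing first-day value, "data from the day closest to the first day of the treatment period should be used". No direction and no maximum distance are given. The next paragraph of 7.4, on LOCF for mean Hb, does fix direction: it reaches back only to earlier visits and never to the first day.

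Section 7.2 of both SAPs confines visit data to the windows in protocol Table 9.1-1 and says values "should not be imputed with those outside the permitted range". For equidistant values, "data for the efficacy and safety evaluations should be adopted before and after the reference date, respectively". Table 9.1-1 gives no window for the first day.

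On the order of testing and dosing, the SAP schedule notes state: "The first dose should be administered after completion of the scheduled tests on the first day of the treatment period". Any later visit is therefore on treatment.

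Protocol 9.2.3 sets the sampling:
- Hepcidin: "Blood sampling and measurement of hepcidin will be performed on the first day of the treatment period", next at Week 2.
- EPO: "Blood sampling and measurement of EPO will be performed on the first day of the treatment period", next at Week 2.
- EQ-5D-5L and KDQOL: first day, next at Week 12.
- Hb: "on the first day of the screening period, screening period Visit 2, the first day of the treatment period, Weeks 2" and onward.

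All four are also collected at discontinuation. Protocol 5.2 adds: "Maximum screening period time is 6 weeks".

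**The concern.** A baseline should be measured before treatment. A closest-day search that runs in both directions can return a value already moved by study drug. That value then acts as the reference for the subject's change scores and as the covariate in the baseline-adjusted models. The subject's response is partly removed from the very quantity meant to measure it. Where the arms respond differently, the contrast between them is diluted as well. Hepcidin, EPO and QOL are most exposed, because their schedule offers no earlier value for the rule to find.

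**Working it through.** **The plan's own figure.** SAP 2.4 claims more than 95% probability of success with 150 per group, SD 1.73 g/dL, true difference 0 and margin −0.75 g/dL.
- Standard error = 1.73 × √(2/150) = 0.1998.
- 0.75 / 0.1998 = 3.754, and 3.754 − 1.960 = 1.794, giving power 0.964.
- Simulating the joint criterion (MT-6548 interval inside the target range, and non-inferiority) gives 0.963.

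The figure is reproduced, and this point does not change it.

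**Which value the rule picks.** Let g be the days from the last usable pre-dose value to Day 0, and w the day of the Week 2 visit (11 to 17 in Table 9.1-1). The rule picks Week 2 when g > w.
- *Hepcidin, EPO:* no pre-dose value is scheduled other than Day 0, so the closest scheduled value is Week 2, or the discontinuation visit if earlier.
- *QOL:* likewise, Week 12 or an earlier discontinuation visit.
- *Hb:* two screening visits. If g ≤ 10, screening always wins. If g ≥ 18, an in-window Week 2 value always wins. In between it depends on w. The screening cap allows up to 42 days from the first screening day.
- *Iron indices, other haematology, biochemistry, CRP:* sampled on the first screening day, while Visit 2 measures only Hb (schedule note [j]). Unless re-tested, g is the whole screening length, so g > w arises more readily than for Hb.
- *Exact ties:* 7.4 does not say. If the 7.2 rule were carried over, the earlier value would serve efficacy and the later, on-treatment value would serve safety.

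**Effect on change from baseline.** Let D_v be an arm's true mean change at the visit that supplies the value, D_w its true mean change at a later visit, and m the share of the arm substituted, assumed unrelated to response.
- Substituted subject: change = 0 at visit v; change is off by −D_v at visit w.
- Arm mean at v: (1 − m) × D_v.
- Arm mean at w: D_w − m × D_v.

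With m = 5%, 95% of the true mean change remains at visit v. In Hb units, with m from 1% to 10% and D_v from −0.25 to −1.0 g/dL (all assumed), the later-visit mean moves by 0.01 × 0.25 = 0.0025 up to 0.10 × 1.0 = 0.10 g/dL.

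**Effect on baseline-adjusted comparisons.** Let Δ_v be the between-group difference at the supplying visit and β the slope of response on baseline, with the same m in both arms. Substitution moves the baseline difference by m × Δ_v, so the adjusted difference moves by −β × m × Δ_v, treating β as fixed. For the primary Hb model, with assumed β from 0.3 to 0.6, m from 1% to 10% and |Δ_v| from 0.25 to 1.0 g/dL:
- smallest: 0.3 × 0.01 × 0.25 = 0.00075, about 0.001 g/dL;
- largest: 0.6 × 0.10 × 1.0 = 0.06 g/dL, or 0.06 / 0.75 = 8% of the margin.

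If MT-6548 is the lower arm at that visit, the shift is towards non-inferiority. If Δ_v is 0, it vanishes.

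The same expression holds when the response is change. The raw difference moves by −m × Δ_v and the slope becomes β − 1, so the net shift is −m × Δ_v − (β − 1) × m × Δ_v = −β × m × Δ_v. Change tables and paired tests thus carry the full m × D_v effect, and the adjusted group comparisons carry β times the corresponding between-group effect.

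**The case against.** The best defence is that the rule will seldom operate. First-day tests are to be finished before dosing, so a missing value should mainly mean a lost or invalid sample. Hb has a second screening visit and possible re-tests. Hepcidin, EPO and QOL are other endpoints, which Phase 1 SAP 8.5.4.7 treats as exploratory together with the secondary endpoints. A sensible programmer might take closest to mean closest before dosing. The sentence preceding the rule also bars imputed data from the MMRM, which could be read as shielding that model.

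The argument on frequency stands: the documents give no share missing, and it is probably small. The argument on wording does not. Section 7.4 states direction where it wants one, and section 7 refers to the case review meeting only handling it has not already specified. Barring imputed data from the MMRM does not clearly reach the baseline, since the next sentence supplies a substitute to serve as the first-day value. Protocol 13.2 has no baseline rule that would settle it.

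A reader might also infer more than the documents support:
- *That every change score is affected.* Change in iron dose uses the screening-period mean as its baseline (Phase 1 SAP 8.5.3(5), final SAP 8.5.2(5)).
- *That the substitute is always Week 2 or Week 12.* A discontinuation visit, or an unscheduled pre-dose sample, could be closer.
- *That only Hb and the iron indices have a screening value.* Protocol 9.2.3 and 9.2.4.1 also give one for other haematology, biochemistry and CRP.

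**Conclusion.** The rule as written admits on-treatment baselines and should be corrected in both SAPs. For hepcidin, EPO and QOL an on-treatment value is the only scheduled substitute. For items with a screening sample it is possible, depending on the length of screening. The consequence is zero change at the supplying visit and a carried error later, in a number of subjects the documents do not give. Exploratory change-from-baseline results bear most of it, including the between-group comparisons.

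It might be inferred that the primary non-inferiority conclusion is in danger. That is not supported: the primary response is Hb itself, baseline enters only as a covariate, and even the largest assumed combination above moves the estimate by 0.06 g/dL. These sizes rest on assumed m, D_v, Δ_v and β, and on missingness unrelated to response.

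**What to change.** In section 7.4 of both SAPs, replace the closest-day sentence with one stating that a missing first-day value is replaced by the latest value measured before the first dose, that baseline stays missing if there is none, and that a post-dose value is never used. Add that this is the stated exception to the window rule in 7.2. If tables have already been produced under the present rule, count the subjects given a post-dose baseline and rerun the affected outputs.

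The drafting cost is a sentence per SAP. The analytical cost is that a subject with no pre-dose value leaves both the change tables and the baseline-adjusted MMRM for that marker, which is a complete-case exclusion. For hepcidin, EPO and QOL that normally means every subject whose first-day value is missing. The number should be reported by arm. Hb and the other items with a screening sample should lose few, if any.
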